We will analyze the primary outcome (proportion of hearts donated) for each OPO individually. Sample sizes will vary between OPOs, so we may only have power to detect large effect sizes. Still, these OPO-specific analyses could provide valuable insights about trends at each OPO.

We will perform prespecified subgroup analyses of:

1. Time to start < 12 hours vs. > 12 hours from BD determination
2. EF result (normal, > 50%, abnormal ≤ 50%)

Methods in analysis to handle protocol non-adherence and any statistical methods to handle missing data {20c}

Donors who are not managed according to the protocol (e.g., not managed properly on T4) will be included in the initial analyses following an intent-to-treat model. Subsequent analyses may exclude those cases in order to evaluate the impact of the protocol on donors who completed it successfully.

Plans to give access to the full protocol, participant level-data and statistical code {31c}

The participant-level (donor) dataset will be made available to all study investigators and their respective OPOs. It may be provided to other OPOs, on request. No recipient outcome data will be shared.

Oversight and monitoring

Composition of the coordinating center and trial steering committee {5d}

The coordinating center is comprised of the study PIs and the central study statistician. The coordinating center will be responsible for oversight of the study. The study statistician will review data entered by study sites for completeness and perform periodic checks for accuracy. The central study coordinator will ensure transfer of additional donor-related data and demographics for each enrolled donor to the central database on a quarterly basis. The respective study OPOs will provide donor data only and not be involved in collecting or analyzing recipient data.

Composition of the data monitoring committee, its role and reporting structure {21a}

The data and safety monitoring committee (DSMC) will be composed of several experienced but independent transplant researchers covering a wide range of expertise.

DSMC Member	Expertise	Institutional Affiliation
[name], PhD CHAIR	Transplant Physician and Researcher SRTR senior scientist	Professor of Medicine with tenure, Co-director of Clinical Research, Medical Director of Living Donation, SSM Health Saint Louis University Transplant Center
[name]	Thoracic Transplant Surgeon (Pediatrics)	Assistant Professor, Department of Surgery, University of Cincinnati
[name]	Transplant Researcher and Statistician SRTR senior scientist	Professor of Surgery with tenure, Director of Clinical Research, SSM Health Saint Louis University Transplant Center
[name], MB,ChB, DA, FNCS	Medical director of organ procurement organization	Professor and Chief of Anesthesiology, Harborview Medical Center, University of Washington Medicine Medical Director, LifeCenter Northwest OPO
[name]	Medical Ethicist	Professor and Director, Albert Gnaegi Center for Health Care Ethics, Saint Louis University
[name], MS	Transplant Epidemiology and Statistical Analysis	Director, Scientific Registry of Transplant Recipients Director, Transplant Epidemiology, Hennepin Healthcare Research Institute

The DSMC statistician ([name]) will analyze the primary outcome and primary safety data at the time of the interim analysis. These results will be shared with the entire DSMC, who will discuss and provide a recommendation on whether to continue recruitment or whether to terminate the study. The DSMC members are independent from the study investigators and are not involved in the procedures of the study in other than this review and the review of any serious safety events.

Adverse event reporting and harms {22}

Study data forms include prospective ascertainment of adverse events entered by the organ procurement coordinators caring for each donor (events listed under *Outcomes, Safety Endpoints* and shown on forms provided in Appendix A). Any events deemed either related or potentially related to the study drug infusion will be reviewed by the site coordinator. The site coordinator will report all AEs that are unanticipated and/or serious to the central site, within 72 hours, for further review. This includes all cases of cardiac arrest or donor instability leading to loss of the donor prior to organ recovery. These events, with narrative review, will be forwarded to the DSMB for review within one week. Incidence of all AEs (by study group) will be provided to the DSMB monthly and also be analyzed as part of the interim safety analysis. In addition, outcomes in the recipients receiving hearts from study participants will be analyzed in the interim analysis to ensure non-inferior graft function and survival.

Frequency and plans for auditing trial conduct {23}

The study statistician (in consultation with the study coordinator and study PI) will audit data and conduct of the trial and oversee and feedback given to each site coordinator.

Plans for communicating important protocol amendments to relevant parties (e.g. trial participants, ethical committees) {25}

Any important amendments to the protocol will be communicated to each study site within one week of the change. These will also be updated on clinicaltrials.gov.

Dissemination plans {31a}

The final study results will be presented internally at the meeting of investigators (part of the Organ Donation Research Council at AOPO) and communicated to the OPO community using the AOPO-plus (restricted) web portal. Findings will be presented in abstract form with plans for simultaneous publication at a major transplantation meeting.

Discussion

This trial was discussed with at the AOPO councils: of medical directors and of the Organ Donation Research Council. Feedback from these groups was incorporated into the study protocol. All OPOs were invited to participate and sent a survey to gauge interest.

Trial status

Recruitment began on : 01 December, 2020

Anticipated date of study completion: 31 December, 2022

Acknowledgements

We would like to acknowledge all the organ procurement coordinators who will perform the essential functions of this study and for caring for each of the donors involved in the study. We would also like to acknowledge each of the site coordinator for the study who collected all the data and ensured adherence to the study protocols and procedures.

Authors' contributions {31b}

All site investigators who participate in the study planning, conduct, and review study results and analyses are eligible to be authors on manuscripts resulting from the study. No outside professional writers or consultants will be utilized. The study statistician and central coordinator will also be included as authors. All these meet the criteria for authorship laid out by the International Committee of Medical Journal Editors. Any other people meeting those criteria will also be invited as co-authors. All authors will read and approve the final manuscript(s).

Funding {4}

No specific funding or financial support is provided to the PIs for performance of this study. However, administrative support will be provided by the study sponsor for effort to coordinate the study and perform statistical analyses. The sponsor will not have access to the primary study data or be involved in its analysis

or interpretation. The sponsor will also not be involved in the writing of the manuscript.

Availability of data and materials {29}

The principal investigator will have final ownership over the dataset for this study. Data will be made available to any OPOs participating in the study and to other OPOs upon reasonable request.

Ethics approval and consent to participate {24}

This trial will not study or collect identifiable data on any human subjects. All donors enrolled in this study have been declared dead by neurologic criteria. However, this donor management study will be approved by the research/ethics committees at each participating OPO site. The study first received determination of non-human subjects status from the *Human Research Protection Office* (HRPO) at Washington University in St. Louis (the academic affiliation of the PI). The individual OPOs will not be collecting data on recipients and so will not be engaged in human subjects' research. However, recipient outcome is a key safety endpoint for this study. The central study coordinators will use the UNOS IDs to obtain de-identified recipient outcome data through UNOS/SRTR. As the recipients' are human subjects, in order to collect recipient outcome data, we have obtained a waiver of recipient consent from the HRPO at the coordinating site. The collection of de-identified recipient outcomes, as outlined, does not pose more than minimal risk to their privacy or safety. The study will not influence how hearts are allocated to particular recipients or means of allocation. Recipient consent would not be feasible at the time of study randomization as this occurs before heart allocation has begun, when the status of the heart and the identity of the recipient is unknown. The study intervention (T4, a standard practice in donor management) will be disclosed as part of the DonorNet platform that transplant centers/surgeons review. Although we do not mandate that information on the study and intervention be directly disclosed to those individuals ultimately receiving the donor hearts, this can be provided to recipients at their discretion. Furthermore, the use of T4 (or not) is not routinely disclosed in standard practice and so this was not felt to be a significant barrier to their autonomy and decision-making. Furthermore, we will monitor for any negative impact on recipients (as a group) through our interim analysis (as overseen by the DSMC) and halt the study if one group exhibits fewer hearts transplanted or worse graft outcomes.

Consent for publication {32}

Not applicable

Competing interests {28}

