Secondary per-protocol analysis expanded to also be performed for safety outcome of graft survival	Primary analysis remains intention-to-treat but per-protocol analysis may be useful to demonstrate true effect of receiving agent on safety.	Statistical methods
Modified analysis of time-to-event outcomes to utilize Cox regression	This approach allows adjustment for covariates in constructing Hazard Ratios	Statistical methods
Count outcome data (i.e. number of organs transplanted) will be analyzed using generalized estimating equations	This is a more flexible approach than pre-specifying Poisson model for comparison of groups	Statistical methods
Better outline the process of safeguarding recipients as human subjects, including basis for waiver of recipient consent and monitoring for any safety concerns (e.g. interim analysis, oversight by DSMC)	Recipients are human subjects and it is important to clearly delineate how their privacy and health is protected in this trial	Ethics approval and consent to participate

Protocol Summary

Title:	A Multicenter Randomized Placebo-Controlled Trial of Intravenous Thyroxine for Heart-Eligible Brain Dead Organ Donors
Precis:	This randomized non-blinded study will compare intravenous thyroxine (T4) to saline placebo in 800 brain dead organ donors who have provided authorization for research and are eligible for heart transplantation based on age and lack of exclusions
Objectives	
Primary: Intravenous thyroxine (T4) will increase the proportion of hearts transplanted when given early after brain death to heart-eligible hemodynamically unstable potential organ donors
 
Safety: Hearts transplanted from donors receiving T4 will have non-inferior 30-day graft survival to those from the placebo group
 
Secondary: T4 will reduce time to wean off vasopressors and improve cardiac ejection fraction

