Primary: Intravenous thyroxine (T4) will increase the proportion of hearts transplanted when given early after brain death to heart-eligible hemodynamically unstable potential organ donors

Safety: Hearts transplanted from donors receiving T4 will have non-inferior graft survival to those from the placebo group at 30-days

Secondary: T4 will reduce time to wean off vasopressors and improve cardiac ejection fraction

Trial design {8}

Randomized in parallel groups to intravenous thyroxine or saline placebo in 1:1 ratio

Randomization will be in blocks, stratified by OPO site, allowing each site to serve as its own control (given heterogeneity in donor management protocols between OPOs)

Administration of study drug or placebo will not be blinded

Methods: Participants, interventions and outcomes

Study setting {9}

This study will be performed under the auspices of various Organ Procurement Organizations (OPOs) across the country (list of active sites available on clinicaltrials.gov). Participants will be patients already declared dead by neurologic criteria (i.e. brain dead) and who have provided authorization (first-person or by living surrogates) for both organ donation and for research. They may be physically located either/both in the hospitals in which they were declared and/or at an independent recovery/donor management facility of the OPO. The donor component has been deemed not to involve human subjects research and participating hospitals and OPOs are therefore not engaged in human subjects' research. The coordinating site (Washington University in St. Louis) will be the research site responsible for collecting recipient outcome data. A waiver of consent has been obtained for de-identified collection of this human recipient data.

Eligibility criteria {10}

Inclusion Criteria:

1. Declared dead by neurologic criteria
2. Provided authorization for organ donation and for research
3. Donor age of 14-55 years (inclusive) and weight \geq 45 kg (100 lbs)
4. On one or more vasopressor and/or inotropes (not including vasopressin)

Exclusion Criteria:

1. Brain death declared $>$ 24 hours prior
2. Known CAD or MI (by history, EKG, or previous cardiac cath)*
3. Significant valvular heart disease (by history of echo)*
4. Prior sternotomy or cardiac surgery*
5. Donor at VA hospital
6. Received intravenous or oral thyroid hormone in the past month
7. Known HIV+ status

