There will be a one-month run-in period at each site where screening logs will be checked by the site and central study coordinators for completeness and accuracy. They will review all cases where donors were not enrolled within 24 hours or if other reasons for ineligibility were provided and provide feedback. The site and study coordinators will have weekly conference calls for the first month (and then monthly thereafter) to discuss issues with adherence. They will also provide feedback to individual OPO personnel if study protocols are violated. The study statistician will perform monthly audits of study data for completeness.

Relevant concomitant care permitted or prohibited during the trial {11d}

All standard OPO donor management practices will be continued throughout the study period until and including organ allocation and recovery. The only intervention prohibited is administration of thyroid hormone to those donors allocated to the placebo group for the first 12 hours after randomization.

Provisions for post-trial care {30}

Data collection on non-human organ donors ends at time of organ procurement or end of donor management (for authorized brain-dead potential donors who do not go on to donate organs).

Outcomes {12}

The primary outcome for this study is the proportion of hearts transplanted (the number of hearts transplanted divided by the total number of potential donors – including those authorized but not recovered).

The primary safety outcome for this study is 30-day graft survival in those receiving hearts from those enrolled in this study. This is defined by patient survival with the originally transplanted heart and no mechanical circulatory support. It will be assessed primarily at 30-days but also at 1-year.

Secondary outcomes will include:

1. Time from randomization to weaning off vasopressors: defined as being off all vasoactive agents, except for vasopressin (≤ 1 U/hr)
2. Proportion weaned off vasopressors by 12-hours (same criteria as #1)
3. Vasopressor-inotrope score at 12-hours (excluding vasopressin ≤ 1 unit/hour)
4. Time achieving hemodynamic stability adequate to order first echocardiography
5. Ejection fraction measured on first donor echocardiography
6. Lungs and total thoracic organs transplanted
7. Total number of organs transplanted

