Our plans for analyzing the secondary outcomes are as follows: for outcome measures that are time-to-event variables such as time to get off vasopressors and time to order first echo, we will perform Cox regression model to assess Hazard Ratio (95% confidence interval) between groups. We will calculate the vasopressor-inotrope score, VIS (27) as: $VIS = \text{dopamine dose } (\mu\text{g/kg/min}) + \text{dobutamine dose } (\mu\text{g/kg/min}) + 100 \times \text{epinephrine dose } (\mu\text{g/kg/min}) + 100 \times \text{norepinephrine dose } (\mu\text{g/kg/min}) + 10 \times \text{milrinone dose } (\mu\text{g/kg/min}) + 100 \times \text{phenylephrine dose } (\mu\text{g/kg/min}) + 10,000 \times \text{vasopressin dose } (\text{U/kg/min} - \text{only for doses } > 1 \text{ U/hour})$. We will compare the decrease in VIS from start of thyroid hormone or saline infusion until 12-hours (end of study infusion), using analysis of covariate method with predictor variables that include the baseline score and the treatment groups and adjusting for site effect. Cardiac ejection fraction will be evaluated using a linear mixed model adjusting for random site effect. If normality assumption is violated, data transformation will be performed. Count data regarding thoracic and total organs transplanted will be compared using Generalized Estimating Equations, with study group as the independent variable and expected organs transplanted as a covariate. All secondary outcome analyses will be two-tailed test at a significance level of 0.05.

Interim analyses {21b}

The DSMC statistician will perform one interim analysis when 376 donors have been enrolled with evaluable data. The trial may be terminated early if, based on the judgement of the DSMC, the interim findings

demonstrate either superiority or clear inferiority of T4 treatment compared to placebo (at a threshold of 0.01). The trial may also be terminated if there is inferiority of graft outcomes in either group, observed at 30-days in those hearts transplanted and observed for this period. The DSMC will provide recommendations to the study PIs, who will make final decisions about whether to stop or continue the trial.

Methods for additional analyses (e.g. subgroup analyses) {20b}

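### The Cox models for weaning and first echo order name no baseline covariate, and the 12-hour weaning proportion has no stated model, so the precision available from the baseline vasopressor-inotrope score goes unused

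*Combined protocol and SAP*

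**What the plan says.** **Entry.** Eligibility criteria {10}, inclusion 4, reads "On one or more vasopressor and/or inotropes (not including vasopressin", with no floor on dose, score or number of agents. Trial design {8} stratifies randomization by OPO site only.

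**Objective and outcomes.** The secondary objective is "T4 will reduce time to wean off vasopressors and improve cardiac ejection fraction". Outcomes {12} lists first "Time from randomization to weaning off vasopressors: defined as being off all vasoactive agents, except for vasopressin" (at up to 1 U/hr), and second "Proportion weaned off vasopressors by 12-hours (same criteria as #1".

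**Analysis.** Statistical methods {20a} says of the time-to-event outcomes that "we will perform Cox regression model to assess Hazard Ratio (95% confidence interval) between groups". It names no covariate, stratum or site term there, and no method for the 12-hour proportion. The next analysis in the same paragraph, change in VIS to 12 hours, is an analysis of covariance with "predictor variables that include the baseline score and the treatment groups", plus site. Age and blood type are prespecified for the primary outcome model only. Secondary tests are two-sided at 0.05.

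**The concern.** The weaning endpoint is reached when non-vasopressin support falls to zero. How much support a donor starts on is therefore plausibly a strong predictor of when that happens and of whether it happens within 12 hours. The plan uses entry support as a covariate for one measure of vasopressor need (VIS change) but does not name it for the two weaning outcomes or for time to first echo order.

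Two things are at stake. The first is precision: omitting a strong predictor from a Cox or logistic model moves a non-null estimate toward 1 and lowers power. The second is prespecification: if covariates are to be added but none are listed, they will be chosen after data exist, in a trial where care providers know the allocation.

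**Working it through.** **1. The plan's own figure.** The only powered efficacy outcome is hearts transplanted, 35% vs 45%, one-sided 0.025, 80% power. With mean proportion 0.40:

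n = [1.96·√(2·0.40·0.60) + 0.8416·√(0.35·0.65 + 0.45·0.55)]² / 0.10² = (1.358 + 0.580)² / 0.01 ≈ 376 per group, 752 in total.

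This matches Sample size {14}, and the present point does not touch it. The documents give no hazard ratio, event count or power for weaning.

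**2. Why omission attenuates.** Donors who are easy to wean leave the risk set first, and faster in the arm that weans faster. The donors still at risk in that arm are then increasingly the hard-to-wean ones, and the unadjusted ratio drifts toward 1. With no treatment effect there is no drift.

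**3. Simulation.** Every input below is an assumption except the numbers of donors (800 and 752), 1:1 allocation and the two-sided 0.05 level. Both simulations use exponential weaning times and a standard normal entry-support covariate, correctly modelled in the adjusted fit.

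- Simulation A: 800 donors, control hazard 0.06/h, censoring at 36 h, 2,000 runs per setting.
- Simulation B: 752 donors, control median 12 h at average support, censoring at 24 h, 600 runs per setting (Monte Carlo error of power up to about 2 points).

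Calibration of B: at a hazard ratio (HR) of 1.25 with no covariate effect, 79% wean, about 0.79 × 752 = 594 events. Schoenfeld's formula gives 75.2% power at 560 events and 80.6% at 640. The simulation gives 78.0%, which fits.

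Results at conditional HR 1.25. The first column is the absolute log-hazard change per SD of entry support. The second is exp(4 × that value), the ratio of weaning hazards between donors 2 SD below and 2 SD above the mean.

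| Effect per SD | Hazard range | Simulation | Unadjusted HR | Power unadjusted | Power adjusted | Loss (points) |
|---|---|---|---|---|---|---|
| 0.25 | 2.7-fold | B | 1.24 | 72.7% | 76.7% | 4 |
| 0.3 | 3.3-fold | A | 1.24 | 80% | 85% | 5 |
| 0.5 | 7.4-fold | A | 1.22 | 73% | 83% | 10 |
| 0.5 | 7.4-fold | B | 1.23 | 69.5% | 79.5% | 10 |
| 0.7 | 16-fold | A | 1.19 | 62% | 83% | 21 |
| 0.75 | 20-fold | B | 1.19 | 54.8% | 75.3% | 21 |
| 1.0 | 55-fold | A | 1.16 | 48% | 81% | 33 |
| 1.0 | 55-fold | B | 1.17 | 45.7% | 76.8% | 31 |

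At conditional HR 1.30 (simulation B), the losses at 0.25, 0.5, 0.75 and 1.0 are about 2, 9, 18 and 27 points. If entry support is not prognostic, there is no difference.

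**4. Weaned by 12 hours** (simulation B, logistic model). Across the same four strengths, the gain from adjustment is 0.8, 4.2, 8.5 and 12.5 points at HR 1.25, and 2.2, 3.8, 8.3 and 13.8 points at HR 1.30.

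**5. Type I error.** At HR 1.0 the unadjusted Cox model rejected in 5.0%, 4.7%, 5.7%, 6.2% and 2.7% of runs over the five covariate strengths (0 to 1.0). The mean HR stayed between 0.99 and 1.00. There is no pattern of inflation.

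**6. Chance imbalance.** With 400 per arm, the standard error of the difference in a standardised covariate is √(2/400) = 0.071 SD. At 0.5 per SD, one standard error shifts the log HR by 0.5 × 0.071 = 0.035, against ln 1.25 = 0.223. A two-standard-error imbalance (0.14 SD) shifts it by 0.07, about 7%.

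Time to first echo order was not simulated, nor was any gain from adding site.

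**The case against.** **Inclusion 4 does what it is meant to do.** The abstract describes donors who require vasopressor support, and the criterion implements that. A reader might infer that the missing dose floor is a design error. The documents do not support this: the criterion only explains why entry support may vary.

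**The unadjusted analysis is valid.** This stands. The smaller unadjusted HR is largely the difference between a marginal and a conditional effect, and chance imbalance is already reflected in the confidence interval. A reader might call the result biased or the test invalid; neither follows.

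**Adjustment may be intended.** The v.3.0 change table justifies Cox regression with "This approach allows adjustment for covariates in constructing Hazard Ratios". A reader might set this against the methods text as a contradiction, or say that the plan ignores entry dose. Neither is fair. A change table that differs from the current text is not an error, and this one suggests that adjustment was in mind. What stands is that the current text lists no covariate.

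**Vasopressor burden already has a baseline-adjusted test.** VIS change is analysed with baseline score and site. This mitigates the gap, but it does not carry over to the weaning outcomes.

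**The large losses need strong assumptions.** Also true. A 30-point loss needs a roughly 55-fold range of weaning hazard between donors 2 SD below and above the mean.

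**Conclusion.** The concern holds as a matter of precision and prespecification. Two Cox analyses name no baseline covariate, and one binary outcome has no stated model, in a section that already derives the relevant baseline score and uses it next door. At an assumed conditional HR of 1.25, the cost in power for time to wean is about 4 to 5 points if VIS is weakly prognostic, about 10 if moderately so, and about 30 if very strongly so. For the 12-hour proportion it is roughly 1 to 14 points over HRs of 1.25 and 1.30. These figures rest on assumed weaning times, follow-up, treatment effect and VIS effect, none of which the documents give, and on a correctly specified covariate.

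A reader might also take weaning to be the main secondary objective. The documents name it beside ejection fraction without ranking them, and set no power target for either. The primary outcome and the recipient safety analysis are untouched. The change is worth making because it is almost free, not because the planned analysis would be wrong.

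**What to change.** Leave inclusion 4 as it is. In Statistical methods {20a}:

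- Name baseline VIS and site as covariates in the Cox models for time off vasopressors and time to first echo order. State how site enters, since it is the only stratification factor.
- State a logistic model for weaned by 12 hours with the same covariates.
- Define one baseline time for VIS, no later than the start of infusion, and use it in the VIS-change analysis too. That analysis now counts from the start of infusion, while the weaning clock starts at randomization.
- Enter the score as log(VIS + 1) or as a spline. A plain logarithm fails at zero, and a zero is possible if a donor's only agent is not in the VIS formula.
- Report the adjusted estimates as the main results for these secondary outcomes, with unadjusted estimates alongside.

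Cost: a few lines of analysis text, ideally fixed before any comparison of weaning by group. No new donors or procedures are needed, and the score is already required at the start of infusion. If an earlier baseline is chosen, check that the data flowsheet records doses at that time; the appendix is not in the documents. The small downside is that the adjusted HR and odds ratio are conditional effects and must be labelled so.
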